- Other causes: a group of young women with low ovarian response have normal basal FSH hormone levels in whom there is no apparent cause for this response (Tarlatzis et al., 2003). Many hypotheses have been proposed to explain this condition. However, none have been proven: a decrease in the number of FSH receptors available in the granulosa cells, FSH post-receptor defects, etc.

Strategies aimed at improving the management of responding casualties

Efforts to provide better control of responding casualties have currently focused on a priori identification of responding casualties and modification of existing protocols themselves.

A priori identification of responder casualties

- Antral follicle count by transvaginal ultrasound: Antral follicle count is nowadays considered the best predictor of ovarian response in isolation (Broeckmans et al., 2006). Most authors use as a cut-off point 3-4 antral follicles on the day when pituitary suppression is proven.
- FSH elevation at the beginning of the cycle: In disuse because of its variable sensitivity and specificity.
- Maternal age: The probability of not conceiving the first child within one year increases from 5% in women in the 20-30 age group to 30% in women over 35 (Broeckmans et al., 2006).
- Anti-Müllerian hormone (AMH): recently, it has been proposed that the determination of AMH) in blood could be used as a test of ovarian reserve so that decreased levels would indicate ovarian aging. Its efficacy is similar to that of the antral follicle count (Broeckmans et al., 2006).

Therapeutic modifications aimed at reducing the incidence of low response

Since the beginning of ART application, many different protocols have been proposed to manage patients with low response, obtaining very different results in the further studies published, making it very difficult to conclude them. Increasing the dose of FSH used (Tarlaltzis et al., 2003), the use of recombinant FSH instead of purified urinary FSH (Raga et al., 1999), the use of FSH in the luteal phase (Rombauts et al., 1998), modifications in pituitary desensitization protocols (García-Velasco et al. 2000), or pre-treatment with estrogens or combined oral contraceptives (Fanchin et al., 2005), pre-treatment with androgens (Fábregues et al., 2009). The reality is that none of these interventions have been shown to be effective in increasing the gestation rate in the subgroup of low responders.

New strategy for ovulation stimulation

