The fragmentation of the ovarian cortex in vitro activates the growth of primordial follicles, leading to the appearance of a greater number of antral follicles, which would make it possible to obtain more oocytes after controlled ovarian stimulation in patients with low ovarian response, which would be useful for improving the success rate of IVF in patients with low ovarian response.

3. Objectives

Main objective:

- To assess whether the fragmentation of ovarian cortex increases the pool of antral (potentially stimulable) follicles.

Secondary objectives:

- To analyse whether the proposed intervention improves ovarian response after gonadotrophin stimulation.
- To evaluate the pregnancy rate.

4. Study design

TYPE OF STUDY

Two-phase study:

- Phase 1: Randomised, controlled, single-blinded clinical trial. Sixty patients previously confirmed as low responders according to ESHRE criteria will be randomised to two treatment arms after assessment of ovarian reserve:

- Arm 1 (control): no intervention was performed on the patient.
- Arm 2 (intervention): removal of ovarian cortex by unilateral laparoscopic oophorectomy, fragmentation of ovarian tissue into 2 mm² aliquots. The ovarian tissue was then re-transplanted under the serosa of the tube homolateral to where the cortex was removed.

Subsequently, bi-weekly ultrasound monitoring was performed to determine the number of antral follicles present in both the native ovary and the re-implanted ovary to determine the number of antral follicles. The number of antral follicles in both intervention groups was compared and the number of antral follicles in the native ovary was also compared with the reimplanted one in each of the patients.

- Phase 2 Prospective observational study. A cohort of all patients who participated in phase 1 was formed and followed for six months. Those patients who wished to undergo IVF treatment received standard treatment for low responders. The final objective consisted of assessing the gestation rate in both groups, as well as the parameters related to the reproductive technique.

STUDY POPULATION

Patients affected by infertility requiring treatment by IVF or ICSI and who were confirmed low responders based on the inclusion criteria.

INCLUSION CRITERIA (one must be met)

- At least two episodes of poor ovarian response (≤ 3 oocytes retrieved in a conventional scheme).

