- A previous IVF cycle with ≤ 3 oocytes (following a conventional stimulation protocol) and presence of an abnormal ovarian reserve test (antral follicle count of ≤ 5 or AMH ≤ 5 pM).

EXCLUSION CRITERIA (the presence of one excludes from participation)

- Patients older than 40 years.
- Clinical suspicion of endometriosis.

- Anovulatory patient (defined by the presence of irregular cycles and serum progesterone on day 21 of the cycle of ≤ 10 ng/mL).
- Couples with severe male factor: severe oligoasthenozoospermia, oligoasthenoteratozoospermia and azoospermia.
- All patients who do not voluntarily give their express written consent.

STUDY VARIABLES

PHASE 1

- Antral follicle count at randomisation (per ovary).
- Antral follicle count after intervention/control (per ovary, fortnightly for 6 months).
- Determination of AMH and FSH/E₂ at the time of randomisation.
- AMH, FSH/E₂ determination after intervention/control (per ovary, monthly for 6 months).

PHASE 2

- Number of metaphase II oocytes obtained after ovarian stimulation.
- Number of follicles punctured.
- Total number of oocytes obtained after ovarian stimulation.
- Number of fertilised oocytes.
- Evolution of embryo development.
- Serum oestradiol levels on the day of hCG.
- Total dose of FSH used.
- Necessary days of gonadotrophin stimulation.
- Clinical pregnancies (determined as the presence of the sac after embryo transfer).
- Progressive gestations (those exceeding 12 weeks).

5. Methods

ASSESSMENT OF OVARIAN RESERVE

- Basal and follicular serum determination of steroid hormones: serum determinations of FSH, E₂ and AMH) were performed with a microparticle immunoassay kit integrated into the ABBOTT AxSYM® Plus system and 5.20 software (Abbott Laboratories, Abbot Park, IL, USA).

- Ultrasound determinations: antral follicle counting was performed with a GE iVoluson (General Electric, Spain) equipped with 3D vaginal transducer (6.5-9MHz). Antral follicles were counted on day 2-5 of the menstrual cycle.

REMOVAL AND REIMPLANTATION OF THE CORTEX

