Official Title: Follicle Activation in Patients with Poor Ovarian Response Through Fragmentation of the Ovarian Tissue.

ClinicalTrials.gov.ID: NCT02354963

Document date: 10th April 2022

Statistical Analysis Plan

Statistical Analysis Plan

The allocation of patients to the study groups was performed using a random number generator (www.random.org), the numbers generated were included in a sealed envelope that was opened at the time of patient randomization.

Information on study variables was collected in a data record booklet (DRB) designed specifically for this study. A database was created to contain the information from the CRFs of the included patients and was equipped with internal consistency rules to control for inconsistencies and/or inaccuracies in data collection and tabulation. The internal coherence rules were guaranteed based on index fields that avoid duplicate records, detect out-of-range or suspicious data and prevent the recording of unrelated data. Before the computerization of the data, a thorough review of the data CRFs was carried out to ensure maximum reliability of the record.

Statistical analysis was performed with the SPSS 2.0.0 statistical package. Variables that followed a normal distribution were expressed as mean and standard deviation, and variables that did not follow a normal distribution were described as median and range. Categorical variables were expressed as absolute values and percentages. Observed differences were considered statistically significant if $p < 0.05$. Comparison of quantitative variables was performed using the Student's t-test or U-Mann test, as appropriate. Comparison of categorical variables was performed using the Chi-square or Fisher test, as appropriate.

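### The SAP plans no baseline adjustment for serum AMH, FSH and E2 and does not say whether level or change is tested, so these secondary comparisons are less precise than the collected data allow

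*SAP*

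**What the plan says.** Protocol section 4, Study variables, Phase 1, lists a baseline measurement, "Determination of AMH and FSH/E₂ at the time of randomisation", and a follow-up series, "AMH, FSH/E₂ determination after intervention/control (per ovary, monthly for 6 months". Each woman therefore has one pre-randomisation value and up to six later values per marker.

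The SAP's third paragraph covers every quantitative variable with one sentence: "Comparison of quantitative variables was performed using the Student's t-test or U-Mann test, as appropriate". It sets significance at 0.05 without stating sidedness. The SAP does not mention AMH, FSH or E2. Neither document contains a baseline covariate, a change score, a repeated-measures model, a summary over months or a chosen month for these markers. The comparisons that Protocol section 4 does describe (between arms, and native against reimplanted ovary) concern antral follicles only.

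On sample size, the Protocol says "Sixty patients previously confirmed as low responders according to ESHRE criteria will be randomised to two treatment arms". It gives no allocation ratio, SD, effect size or power.

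**The concern.** Arm 2 has one ovary removed and cortex fragments returned as a graft, while Arm 1 has no intervention. Whether ovarian reserve rises or falls afterwards matters for both benefit and harm. Serum hormones are the only Phase 1 follow-up measures listed that do not depend on an ultrasound count. Protocol section 1 presents AMH as a proposed blood test of reserve in which "decreased levels would indicate ovarian aging".

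Women differ in AMH before anything is done to them. The first entry route sets no AMH limit, and the second can be met through the antral follicle count instead of AMH. To the extent that these differences persist, a plain comparison of follow-up levels leaves them in the error term, although the trial already holds the value that would remove them. With 60 women, a real fall or gain is then harder to detect and its confidence interval is wider than it need be.

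There is also a specification gap. Level or change, and which of six months, are left open for several markers, so the choice could be made after seeing the data.

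**Working it through.** The plan gives no power or precision figure for these markers, so there is none to reproduce. The check compares the analyses that the data would support.

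**Inputs**
- N = 60 (Protocol section 4); 1:1 allocation, so n = 30 per arm, is assumed.
- Alpha 0.05 (SAP); two-sided is assumed.
- Six monthly follow-up values per marker (Protocol section 4).
- True difference d = 0.5 SD: illustrative.
- Correlation rho between baseline and follow-up: not in the documents, varied over 0.3, 0.5 and 0.7.
- Equal variances and no dropout are assumed.

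**Variance factors v, relative to one follow-up level**
- Level: v = 1.
- Change from baseline: v = 2(1 − rho), giving 1.40, 1.00, 0.60.
- ANCOVA at one month: v = 1 − rho², giving 0.91, 0.75, 0.51.
- Mean of six months, unadjusted: v = (1 + 5rho)/6, giving 0.417, 0.583, 0.750.
- Mean of six months, ANCOVA: v = (1 + 5rho)/6 − rho², giving 0.327, 0.333, 0.260.

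The last two assume the same rho between every pair of measurements.

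**Power at one time point**
Non-centrality = d / √(2v/n), referred to a non-central t with 58 df (57 for ANCOVA).
- Level: 0.5/√(2/30) = 1.936, power 47.8%.
- Change: 1.637, 1.936, 2.500, power 36%, 48%, 69%.
- ANCOVA: 2.030, 2.236, 2.712, power 51%, 59%, 76%.

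A simulation of 20,000 trials agrees closely. At rho 0.5 it gave 47%, 48% and 58% for level, change and ANCOVA. At rho 0.7 it gave 47%, 69% and 75%.

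**95% half-width in SD units, 1.96 × √(2v/n)**

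| Analysis | rho 0.3 | rho 0.5 | rho 0.7 |
|---|---|---|---|
| Level, one month | 0.506 | 0.506 | 0.506 |
| Change, one month | 0.599 | 0.506 | 0.392 |
| ANCOVA, one month | 0.483 | 0.438 | 0.361 |
| Mean of six, unadjusted | 0.327 | 0.387 | 0.438 |
| Mean of six, ANCOVA | 0.289 | 0.292 | 0.258 |

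Against a level test, ANCOVA at one month cuts the standard error by 1 − √(1 − rho²): 4.6%, 13.4% and 28.6%. Against a change score it cuts it by 1 − √((1 + rho)/2): 19%, 13% and 8%. ANCOVA on the six-month mean has the shortest interval in every column.

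**On the AMH scale.** Suppose the SD of log AMH is 0.8 (an assumption). Then 0.5 SD is 0.4 on the log scale, and exp(−0.4) = 0.67, a one-third fall. The 95% interval for the AMH ratio at one month is ×/÷ exp(t × 0.8 × √(2v/30)): 1.51 for level, and 1.43 or 1.34 for ANCOVA at rho 0.5 or 0.7.

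**Selection of month.** Six separate tests at 0.05 would give a false-positive chance of 1 − 0.95⁶ = 26% per marker if they were independent. Monthly values are correlated, so the true figure is lower.

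**The case against.** A reader might infer that the SAP tests the follow-up level and that a t-test or Mann-Whitney test cannot use the baseline. The documents do not support that. The SAP does not say what quantity is tested, and either test applied to change from randomisation fits its wording. At rho 0.7 that alternative already has 69% power against 76% for ANCOVA, a gain of 7 points. The step from 48% to 76% applies only if level is tested and rho is as high as 0.7. This objection stands. It does not rescue the plan, because a change score is worse than level when rho is below 0.5, and ANCOVA is ahead of both at each rho examined.

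It is also fair to say that AMH and FSH/E2 are listed variables and do not appear in the objectives, which concern antral follicles, ovarian response and pregnancy. The SAP's generic sentence leaves the same gap for the antral follicle count, the main outcome. The entry criteria permit a wide AMH spread but do not show one, and wide spread would not by itself mean a high rho. Protocol section 1 describes raised early-cycle FSH as a test that has fallen out of use because its performance varies, so FSH should not be promoted to a reserve measure. All of this limits the weight of the point.

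Finally, Protocol section 4 allows women to have IVF during a six-month follow-up in Phase 2. It does not say whether this overlaps the monthly hormone series. If it does, the SAP must say how those months enter any average.

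**Conclusion.** The point holds as one of efficiency and pre-specification for secondary, supportive outcomes. Baseline and monthly serum values are collected, and no planned analysis is stated to use the baseline or to combine the months. At one time point with d = 0.5 and 30 per arm, baseline adjustment raises power over a level test by about 4, 12 and 28 points at rho 0.3, 0.5 and 0.7. Over a change score it adds about 15, 12 and 7 points. Which comparison applies is unknown, because the SAP does not choose. The size rests on assumed rho, 1:1 allocation, a two-sided test and no attrition. The further gain from averaging six months also needs the arm difference to be similar across months.

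A reader might go on to infer that the planned test is biased, or that a non-significant fall would be reported as no difference. Neither follows: the unadjusted test is valid under randomisation, and the SAP contains no such reporting rule.

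**What to change.** Add a paragraph on the hormone outcomes to the SAP:

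- **Model.** Compare arms on log AMH, and likewise on log FSH and log E2, with the woman's own log value at randomisation as covariate. Use either ANCOVA on the mean of the six monthly log values or a repeated-measures model over months 1 to 6. Also report month 6.
- **Estimate.** Report the ratio of geometric means, Arm 2 to Arm 1, with its 95% CI.
- **Assay limit.** State in advance how values below the limit are handled before logs are taken.
- **Role.** Treat the results as supportive of the antral follicle count, with AMH as the serum reserve marker and FSH/E2 descriptive.
- **Months with ovarian stimulation.** If any fall within the series, say how they are handled.

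In Protocol section 4, reconcile the two hormone lines. The follow-up values are labelled per ovary and the baseline values are not. A serum level belongs to the woman, and the covariate must be on the same footing as the outcome.

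The cost is wording, one degree of freedom and slightly more analysis work. No extra patients or blood samples are needed.
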